### **13.4 New Onset of Chronic Illness**

New Onset of Chronic Illness (NOCI) is defined as diagnosis post-enrollment and vaccination of a new medical condition which is chronic in nature, including those potentially controllable by medication (e.g., diabetes, asthma).

In the summary tables, the total number of subjects having reported at least one NOCI with the proportion and the total number of NOCIs reported will be provided for each treatment arm. For example, the tables will state that X (%) subjects have reported Y events in treatment arm A. Then, they will present the details of NOCIs per SOC and PT with the same information: number (%) of subjects and number of events.

The NOCIs summaries at Day 365 Post-Vaccination will include:

- NOCIs summary by SOC and PT
- NOCIs summary by SOC, PT, and Severity
- NOCIs summary by SOC, PT and Relationship

In the summary tables, NOCIs will be presented by decreasing frequency of number of subjects with event and total events under “overall” treatment arm within each SOC and then similarly by decreasing frequency of number of subjects with event and total events under “overall” treatment arm within each PT.

All NOCIs collected during the follow-up period of the study will also be provided, for each treatment arm, study day, in duration, by severity and relationship to the treatment in by-subject listings.

### **13.5 Adverse Event of Special Interest**

An adverse event of special interest (AESI) (serious or nonserious) is one of scientific and medical concern specific to the Sponsor’s product or program, for which ongoing monitoring and rapid communication by the Investigator to the Sponsor can be appropriate. For this study, AESIs are serious or non-serious adverse events of scientific and medical concern with potential immune-mediated medical conditions as well as events associated with thrombosis and thrombocytopenia as listed in Table 11 in the protocol.

In the summary tables, the total number of subjects having reported at least one AESI with the proportion and the total number of AESIs reported will be provided for each treatment arm. For example, the tables will state that X (%) subjects have reported Y events in treatment arm A. Then, they will present the details of AESIs per SOC and PT with the same information: number (%) of subjects and number of events.

The AESIs summaries at Day 365 Post-Vaccination will include:

- AESIs summary by SOC and PT
- AESIs summary by SOC, PT, and Severity
- AESIs summary by SOC, PT and Relationship

In the summary tables, AESIs will be presented by decreasing frequency of number of subjects with event and total events under “overall” treatment arm within each SOC and then similarly by decreasing frequency of number of subjects with event and total events under “overall” treatment arm within each PT.

All AESIs collected during the follow-up period of the study will also be provided for each treatment arm, study day, in duration, by severity and relationship to the treatment in by-subject listings.

### **13.6 Vital Signs**

The following vital signs measurements will be taken, in a sitting position, on the study day specified in the Schedule of activities:

- Systolic blood pressure (SBP) (mmHg)
- Diastolic blood pressure (DBP) (mmHg)
- Respiratory rate (breaths/min)
- Heart Rate (beats/min)
- Body Temperature (°F)
- Clinical Assessment for each vital sign measurement (as described below)

All vital signs data collected at scheduled and unscheduled visits will be included in the listings, but only results collected as scheduled visits will be included in the summary tables.

The parameter names that will be used in the outputs will comprise of the test name and the unit of measure, for example, ‘Systolic Blood Pressure (mmHg)’. Parameters will be presented in the order defined above within the tables and listings.

Vital signs measurements will present summary statistics for observed values at baseline, each post-baseline and actual change from baseline (last pre-vaccination value) for each parameter and will be summarized as described in [section 3.1](#) (continuous descriptive analysis).

The decimal precision to which the summaries for each displayed parameter will be based on the maximum number of decimals to which the results were reported on the eCRF.

The summary of all the clinical assessments for each parameter table will present counts and percentages for the reported results at baseline and each post-baseline visit/time point. Result categories will be ordered as ‘Normal’, ‘Abnormal Not Clinically Significant (NCS)’ and ‘Abnormal Clinically Significant (CS)’ (categorical descriptive analysis as described in [section 3.1](#)).

All individual Vital Signs results including unscheduled visits and their clinical assessment will be presented, for each treatment arm, by study days, in the by-subject listings.

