Overall, 76 healthy lactating female subjects from 18 years of age or greater and their breastfed infants aged >30 days to 11 months of age will be enrolled and randomly assigned to the three cohorts. The sample size chosen is based on clinical judgment consultation with physicians and a biostatistician, and no formal sample size or power calculation was conducted.

Interim Analysis:

No interim analysis will be conducted for this study.

Safety Monitoring Committee:

A Safety Monitoring Committee (SMC) will be assigned by the Sponsor prior to the beginning of the study and will provide oversight of the study throughout the duration of the study period (Day 1 through Day 365) as needed. Ad hoc meetings will be convened if any predefined stopping rules are met, or any serious vaccine-related events or trends are observed.

Further details regarding data safety monitoring guidelines will be included in the SMC Charter, which is the governing document that supersedes this section of the protocol.

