- Perform an alcohol test and site must confirm negative result before dosing.
- Vital signs will be obtained, including temperature, blood pressure, pulse rate and respiratory rate after resting in a sitting position for at least 5 minutes.
- A targeted, and symptom-directed physical examination will be done for all subjects during the active study period visits. At a minimum, assessments of the skin, respiratory system, cardiovascular system, and GI (abdomen, liver, and spleen) will be included.
- The subject's randomization number will be noted.

- Collect blood, nasal and saliva samples for Immunogenicity assessment prior to study drug administration.
- Site staff member(s) will dispense/administer the investigational product. Please refer to the Pharmacy Manual for further instruction on this process.
- Prior to study drug administration on Day 1, the subject's temperature (oral) will be measured, and a trained member of the site study staff will dispense the tablet(s) constituting the assigned dose to the subject.
- The site staff must observe the subjects for at least 30 minutes after study drug administration for any acute reactions. Any acute reactions are to be recorded in the subject's source documents, on the AE page of the eCRF, as applicable.
- Subjects will be asked to record symptoms of reactogenicity daily for 1 week after study drug administration on Day 1, using the Solicited Symptom Diary; the Solicited Symptom Diary will be collected from the subject on Day 8 and reviewed.
- Subjects will be queried for unsolicited AEs for 28 days following the study drug administration and for SAEs, AESIs and NOCIs for 1 year following the study drug administration.
- Subjects will return to the site on Day 8 and Day 29:
 1. Blood, nasal, and saliva samples will be collected for immunogenicity assessment on Day 8 and Day 29 as specified in the SoA ([Table 1](#)).
 2. Ascertain if the subject is still breastfeeding. Ensure the subject has also collected breastmilk sample and infant stool sample during the timepoints specified in the SoA ([Table 1](#)), if not then remind the subject. Review with the subject how the collection was done and if the samples were properly stored.
 3. Verify understanding of and compliance with protocol requirements for contraception (see [Appendix 4](#)).
- The subject will be asked to contact the site staff or Investigator if an AE (e.g., doctor's visit, emergency room visit) or hospitalization occurs.

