7.1.5 Unscheduled Visit

At the discretion of PI and/or per subject request to evaluate any of the expected reactogenicity symptoms or any unexpected symptoms of concern, a contact must occur as soon as possible between the subject and the Investigator, or a medically qualified member of the study site staff, to assess if an unscheduled visit is required.

This contact will be recorded in the subject's eCRF. If the subject is unable to attend the unscheduled visit, any ongoing reactions must be assessed at the next scheduled visit. Reactogenicity events should be assessed by the Investigator or a medically qualified member of the site staff, such as a study physician or a study nurse, as applicable, to the Investigator's local practice, who will:

- Measure oral temperature.
- Measure the subject's pulse rate (after five minutes of sitting).
- Measure the subject's blood pressure (after five minutes of sitting).
- Assess any events (specify the events of interest) that are present, in accordance with the reactogenicity grading scale.
- Perform a symptom focused physical examination.
- Ask the subject if she attended an emergency room visit or was hospitalized.
- Complete the source documents.
- The Investigator or an authorized designee will complete the eCRF.

The subject will be instructed to contact the site to report any significant illness, AEs, or hospitalization that occurs during the study period.

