## 2.4 Sample Size

A sample size of 76 randomized subjects (30 each in medium and high dose levels and 16 in placebo) is not based on formal statistical testing but rather based on clinical judgement and predicted to yield meaningful safety and immunogenicity results. Placebo was added for safety comparison.

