#### 3.1 General Considerations

All data collected on the electronic case report form (eCRF) will be presented in the data listings and will be sorted by treatment arm, subject number and visit, where applicable. All descriptive summaries will be presented by treatment arm and nominal visit.

All safety and immunogenicity descriptive summaries will be presented by treatment arm and nominal visit.

Unless otherwise stated, the following methods will be applied:

- Continuous variables: Descriptive statistics will include the number of non-missing values (n), arithmetic mean, standard deviation (SD), median, minimum and maximum values.

The minimum and maximum values will be displayed to the same decimal precision as the source data, the arithmetic mean, SD and median values will be displayed to one more decimal than the source data for the specific variable.

95% Confidence Intervals (CIs), mean differences (among treatments and from baseline) and least-square (LS-Means) values will be displayed to one more decimal than the source data for a specific variable. P-values will be displayed to 3 decimal places.

The appropriate precision for derived variables will be determined based on the precision of the data on which the derivations are based, and statistics will be presented in accordance with the above-mentioned rules.

- Categorical variables: Descriptive statistics will include counts and percentages per category. The denominator in all percentage calculations will be the number of subjects in the relevant analysis population with non-missing data, unless specifically stated otherwise. Percentages will be displayed to one decimal place. Proportions will be displayed to 3 decimal places.

95% Confidence Intervals (CIs), difference in proportions and other categorical parameters will be displayed to one decimal place for percentages. Proportions will be displayed to 3 decimal places. p-values will be displayed to 3 decimal places.

- Repeat/unscheduled assessments: Only values collected at scheduled study days/time points will be presented in summary tables. If a repeat assessment was performed, the result from the original assessment will be presented as the result at the specific visit/time point. All collected data will be included in the data listings.

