### 3.3 Inferential Analyses

No formal hypothesis testing is planned.

Descriptive statistics will be used to summarize the safety and immunogenicity data.

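### The vital-sign tables omit unscheduled visits, so a clinically significant blood pressure or pulse reading in the week after dosing that is not also recorded as an AE appears in no by-arm count.

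*SAP*

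**What the plan says.** SAP 13.6 covers systolic and diastolic blood pressure, respiratory rate, heart rate and temperature. Each reading also gets a clinical assessment: normal, abnormal but not clinically significant (NCS), or abnormal and clinically significant (CS). Table 14.3.5.1.1 summarises the values and Table 14.3.5.1.2 the clinical categories, both by treatment arm. For these tables, "only results collected as scheduled visits will be included in the summary tables". SAP 3.1 has the general rule: "Only values collected at scheduled study days/time points will be presented in summary tables".

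The unscheduled readings are kept in a listing: "All individual Vital Signs results including unscheduled visits and their clinical assessment will be presented, for each treatment arm". This is Listing 16.2.8.1.

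Protocol 7.1.5 provides for unscheduled visits, at the investigator's discretion or the woman's request, "to evaluate any of the expected reactogenicity symptoms or any unexpected symptoms of concern". A contact first decides whether a visit is needed. If it is, oral temperature, pulse and blood pressure are measured.

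**The concern.** Readings at unscheduled visits are not a random sample of the week. They exist because a woman had symptoms or an investigator was concerned. The scheduled readings that the tables keep are at Day 8 and Day 29, by which time an acute reaction may have resolved.

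Protocol 11.4.2 includes vital signs in the safety results summarised by treatment group and study visit, and SAP 2.4 says that placebo was included for safety comparison. A by-subject listing sorted by arm gives no counts or percentages. The CS category could therefore read zero in every arm of Table 14.3.5.1.2 while CS blood pressure or pulse readings stand in the listing. A reader of the tables alone would not know.

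**Working it through.** There is no figure in the plan to reproduce. The protocol synopsis says that "no formal sample size or power calculation was conducted", and SAP 3.3 says "No formal hypothesis testing is planned". The check sets the sections side by side.

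**1. When vital signs are scheduled.** The Schedule of Activities (protocol Table 1, repeated in SAP Table 1) marks Screening, Day 1, Day 8 (+2 days) and Day 29 (±2 days). Day 15 is a telephone contact.

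**2. Whether the Day 1 set is post-dose.** It is not. Protocol 7.1.2 has the steps listed ahead of vaccine administration done ahead of it. Among them: "Vital signs will be obtained, including temperature, blood pressure, pulse rate and respiratory rate". The observation of at least 30 minutes after dosing specifies no vital signs. This leaves two scheduled post-dose time points (Day 8 and Day 29) and none between dosing and Day 8.

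**3. Where each measurement can come from between dosing and Day 8**

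| Measurement (SAP 13.6) | Source in that interval, woman still in study | By-arm table it can reach |
|---|---|---|
| Temperature | Daily oral reading with the study thermometer, all women (protocol 7.1.1); also unscheduled visits | Fever by grade, Table 14.3.3.1.3 |
| Systolic and diastolic blood pressure | Unscheduled visits only | None, unless recorded as an AE |
| Heart rate (pulse) | Unscheduled visits only | None, unless recorded as an AE |
| Respiratory rate | Not on the protocol 7.1.5 list | None planned |

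A woman who terminates before Day 8 has the Day 8 procedures, including vital signs, at her early termination visit (protocol 5.2).

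**4. Whether the AE tables close the gap.** The unsolicited TEAE tables (14.3.3.1.4 to 14.3.3.1.6.3) cover Day 1 to Day 29 by arm and are not limited by visit type, so a reading entered as an AE is counted. Neither blood pressure nor pulse is among the nine solicited symptoms in SAP 13.1. The AE definition in protocol 9.1 is general, and no sentence requires a CS vital sign to be recorded as an AE.

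**5. Consistency of the rule.** SAP 3.2 lets unscheduled readings count towards baseline, whereas SAP 3.1 and 13.6 keep them out of the post-dose summaries.

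**6. Scale, by assumption.** The arms are 30, 30 and 16 women (SAP 2.4). Suppose that x of 30 women in one arm have a CS blood pressure or pulse reading at an unscheduled visit before Day 8, that none is recorded as an AE, and that all 30 are normal at Day 8. The documents give no value for x. SAP 13.6 plans only counts and percentages here; the exact (Clopper-Pearson) 95% intervals are added for scale.

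- Day 8 row, for any x: 0/30, interval 0 to 11.6%. The upper limit is 1 − 0.025^(1/30) = 0.116.
- Women with any CS reading, x = 1: 1/30 = 3.3% (0.1 to 17.2%).
- x = 3: 3/30 = 10.0% (2.1 to 26.5%).

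These lines answer different questions. The Day 8 row is correct for Day 8. The others count women found to have a CS reading among those who happened to be measured.

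**The case against.** Several points on the other side stand. Restricting by-visit summaries to scheduled time points is ordinary practice and gives every woman the same measurement opportunities. Protocol 11.4.2 asks for summaries by study visit, which is what these tables provide. Symptom-triggered readings in those rows would make the sampling depend on outcome. Every reading is listed by arm with its clinical assessment, no woman is removed from the tables, and vital signs are not a named primary or secondary endpoint. The fix therefore leaves the by-visit rows alone.

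The best single counter-argument is protocol 9.5.1, which requires all findings in women experiencing AEs to go on an AE page. A CS reading in a symptomatic woman fits that sentence naturally, and if sites apply it so, the TEAE tables will count it. But the sentence does not name vital signs, and solicited symptoms are reported through the diary (protocol Table 7). Whether a pulse or blood pressure reading becomes a separate AE is thus left to the site.

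Two stronger readings are tempting, and the documents support neither. One is that unscheduled visits supply the only vital signs of any kind between dosing and Day 8. They do not: daily oral temperature is mandatory for every woman, and early terminators have a full set. The other is that abnormal readings can never reach an arm-level table. Fever is tabulated by arm and grade, events at an unscheduled visit are assessed on the reactogenicity scale, and anything entered as an AE is counted.

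**Conclusion.** The gap is real but narrow. It concerns blood pressure and pulse, in women who remain in the study, at unscheduled visits between dosing and Day 8, where a CS reading is not also recorded as an AE. Such a reading appears only in Listing 16.2.8.1. The same table rule applies to unscheduled visits between Day 8 and Day 29, although scheduled readings stand at both ends of that interval.

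The conclusion rests on the Day 1 vital signs being taken before dosing, as the step order in protocol 7.1.2 indicates, and on there being no explicit rule that a CS vital sign is an AE.

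Its size cannot be stated, because the documents give neither the expected number of unscheduled visits nor the frequency of CS readings. A reader might take 3/30 in the illustration as the true rate for the week. It is not: the value is assumed, and women without an unscheduled visit have no blood pressure or pulse reading in that interval. This is a small, cheap improvement to safety reporting. No primary endpoint estimate and no sample size consideration changes.

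**What to change.** In SAP 13.6, keep the by-visit rows of scheduled results and add to Table 14.3.5.1.2, by arm, each woman's worst post-dose clinical category (Normal, NCS, CS) for blood pressure and for heart rate. It should run from after dosing on Day 1 to Day 29 and use scheduled and unscheduled readings. Show beside it the number of women per arm with an unscheduled visit, because more visits give more chances of an abnormal reading. Temperature and respiratory rate need no such row: the fever tables cover the first, and the second is not on the unscheduled-visit list.

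SAP 3.1 applies its rule unless otherwise stated, so the exception can be written in 13.6 alone. A sentence saying whether CS vital signs are to be recorded as AEs would close part of the same gap.

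The cost is a short SAP edit and a few table rows. No new data are needed, since SAP 13.6 already lists the unscheduled readings with their clinical assessment. The downside is unequal measurement opportunity between women, which the visit count makes visible.

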### **13.7 Physical Examinations**

Complete and symptom-directed physical examinations will be performed by the PI, on the study days specified in the schedule of activities.

Physical examinations may be performed at various unscheduled time points if deemed necessary.

By-subject data listings will be presented on the study days collected for complete physical examination parameters and Symptom directed physical examination parameters.

### **13.8 Pregnancy Test Results**

A serum pregnancy test and a urine pregnancy test will be performed on the study day specified in the Schedule of activities.

All information related to pregnancy testing (urine and serum based) will be presented, for each treatment arm, by study days, in the by-subject data listings for all subjects.

## 14. IMMUNOGENICITY

Subjects will be analyzed according to the treatment (vaccine) they received. All immunogenicity analyses will be conducted based on the Immunogenicity Analysis set (IS).

Immunogenicity samples will be drawn for all subjects. Immunogenicity analyses will be based upon results from appropriately sized subsets of samples, according to the purpose. The statistical immunogenicity analysis will be primarily based on the evaluable Immunogenicity Analysis Set.

Vaccine induced immunogenicity will be evaluated in subject Breast Milk, serum, saliva, nasal secretions and in participants infants' stool samples. Samples will be collected from all subjects according to the time points specified in the SoA.

The following primary immunogenicity endpoints will be analyzed:

- Serum VP1 specific (GI.1 and GII.4) IgA through the active period measured by Meso Scale Discovery (MSD) assay by dose level
  - Geometric mean concentration (GMC) at Day 1, Day 8 and Day 29
  - Geometric mean fold rise (GMFR) from Day 1 to Day 8 and from Day 1 to Day 29
  - The number and %of subjects in each dose group that had a 2-fold, 3-fold and 4-fold GMC rise or greater in serum VP1 specific IgA (GI.1 and GII.4) between Day 1 and any other timepoint
- Breast Milk VPI specific (GI.1 and GII.4) IgA through the active period measured by MesoScale Discovery (MSD) assay by dose level
  - Geometric mean concentration (GMC) at Day 1, Day 8 and Day 29
  - Geometric mean fold rise (GMFR) from Day 1 to Day 8 and from Day 1 to Day 29
  - The number and %of subjects in each dose group that had a 2-fold, 3-fold and 4-fold GMC rise or greater in breast milk VP1 specific IgA (GI.1 and GII.4) between Day 1 and any other timepoint

The following secondary immunogenicity endpoints will be analyzed:

- Serum VP1 specific (GI.1 and GII.4) IgA through 6 months after study drug dose measured by MesoScale Discovery (MSD) assay by dose level
  - Geometric mean concentration (GMC) at Day 180
  - Geometric mean fold rise (GMFR) from Day 1 to Day 180
  - The number and %of subjects in each dose group that had a 2-fold, 3-fold and 4-fold GMC rise or greater in serum VP1 specific IgG (GI.1 and GII.4) between Day 1 and Day 180
- Breast Milk VP1 specific (GI.1 and GII.4) IgA through 6 months after study drug dose measured by MesoScale Discovery (MSD) by dose level
  - Geometric mean concentration (GMC) at Day 60 and Day 180
  - Geometric mean fold rise (GMFR) from Day 1 to Day 60 and from Day 1 to Day 180
  - the number and %of subjects in each dose group that had a 2-fold, 3-fold and 4-fold GMC rise or greater in serum VP1 specific IgA (GI.1 and GII.4) between Day 1 and any other timepoint
- Serum VP1 specific (GI.1 and GII.4) IgG through 6 months after study drug dose measured by Meso Scale Discovery (MSD) assay by dose level
  - Geometric mean concentration (GMC) at Day 1, Day 8, Day 29, and Day 180
  - Geometric mean fold rise (GMFR) From Day to Day 8, from Day 1 to Day 29, and from Day 1 to Day 180
  - The number and %of subjects in each dose group that had a 2-fold, 3-fold and 4-fold GMC rise or greater in serum VP1 specific IgA (GI.1 and GII.4) between Day 1 and any other timepoint
- Serum Blocking titers 50 (BT50) (GI.1 and GII.4) through 6 months after study drug dose measured by Histo-blood group antigen (HBGA) assay by dose level

- Geometric mean titer (GMT) at Day 1, and Day 29,
- Geometric mean fold rise (GMFR) from Day 1 to Day 29
- The number and %of subjects in each dose group that had a 2-fold, 3-fold and 4-fold GMT rise or greater in BT50 (GI.1 and GII.4) between Day 1 and Day 29

All the above analysis will be repeated for the per protocol set if the difference of sample size between per protocol and immunogenicity set are greater than 20%.

For the Exploratory samples: Saliva VP1 specific (GI.1 and GII.4) IgA, Nasal VP1 specific (GI.1 and GII.4) IgA, Infant stool VP1 specific (GI.1 and GII.4) IgA, Breast Milk Blocking titers 50 (BT50) (GI.1 and GII.4), and Breast Milk Enterocyte culture neutralizing antibody titers (GI.1 and GII.4) the results will be analyzed based on data availability and will be on file at Vaxart, Inc.

